6.8. Multiple Comparisons/Multiplicity

Only one hypothesis test will be performed for the primary analysis. Secondary and exploratory analyses will not be corrected for multiplicity.

7. STUDY SUBJECTS

7.1. Disposition of Subjects

Reasons for screening failures will be summarized in [Table 12](#). The completion status and reasons for early termination or treatment discontinuation will be summarized ([Table 8](#) and [Listing 2](#)). A subject could be discontinued early due to an AE (serious or non-serious), loss to follow-up, non-compliance with study, voluntary withdrawal, withdrawal at the investigator request, termination of the site by the sponsor, termination of the study by the sponsor, death, lack of eligibility at enrollment, inadequate clinical response, or becoming ineligible after enrollment.

Subject disposition and eligibility for analysis will be summarized in a CONSORT flow diagram ([Figure 1](#)).

7.2. Protocol Deviations

A summary of subject-specific protocol deviations will be presented by the reason for the deviation, the deviation category, and treatment group for all subjects ([Table 5](#), [Table 6](#), and [Listing 3](#)). Non-subject specific protocol deviations will be in [Listing 4](#). All subject-specific protocol deviations and non-subject specific protocol deviations will be presented. Major protocol deviations are selected by the PI/DMID and ARLG.

8. EFFICACY EVALUATION

All efficacy variables will be listed by subject. Data will be summarized by treatment group. Continuous efficacy variables will be summarized with the number of observations, mean, median, standard deviation, minimum, and maximum. Categorical efficacy variables will be summarized by number and percent in each category.

All statistical tests are performed at the $\alpha=0.05$ significance level. The primary hypothesis is a one-sided test but uses a two-sided 95% CI to make a conclusion about non-inferiority.

8.1. Primary Efficacy Analysis

The primary efficacy analyses of clinical improvement at D5V will be performed for the ITT analysis population. Clinical Improvement at D5V is defined in Section 3.3.

8.1.1. Primary Analysis of Clinical Improvement at D5V Using ITT Population

The hypotheses corresponding to the primary analysis of this study are:

Null hypothesis: $\pi_{\text{placebo}} - \pi_{\text{azithromycin}} \leq -12.5\%$,

Alternative hypothesis(non-inferiority): $\pi_{\text{placebo}} - \pi_{\text{azithromycin}} > -12.5\%$,

where π represents the probability of clinical improvement at study D5V. 12.5% is the non-inferiority margin used for this study and is also used for all secondary non-inferiority analyses. The primary analysis alone will be used to conclude non-inferiority of placebo to azithromycin, while other analyses are supportive.

The non-inferiority of placebo versus azithromycin with respect to clinical improvement on at D5V using a non-inferiority margin of 12.5%, will be determined for the ITT analysis population using a two-sided 95% CI of the difference in proportions of clinical improvement as constructed using multiple imputation of clinical improvement with linear regression. The study day that D5V occurred on will be included as a covariate. A lower bound of the CI greater than -12.5% will result in the conclusion of non-inferiority of placebo. The imputation model will utilize available information collected at baseline and any completed study visits.

The primary analysis will use multiple imputation with a linear regression model without rounding to impute missing values of clinical improvement at D5V using the ITT population [9 and 10].

Although the linear regression without rounding can sometimes yield implausible imputed values of treatment success, Horton et.al (2003) [10] showed that this method yields an unbiased estimate of the binomial proportion.

- Let Y_1, Y_2, \dots, Y_N be independent and identically distributed (iid) Bernoulli random variables
- Let $p = E(Y_i)$ be the probability of success
- Assume that only n out of the N Bernoulli data points are observed; the rest are missing. For simplicity, assume Let Y_1, Y_2, \dots, Y_n are observed and Let Y_{n+1}, \dots, Y_N are missing. Further assume that data is Missing Completely at Random (MCAR).

For estimating p , the minimum variance unbiased estimate (MVUE) of p denoted by \hat{p} which is simply the mean of observed data, i.e.,

$$\hat{p} = \frac{1}{n} \sum_{i=1}^n Y_i$$

Rubin and Schenker (1986) [11] proposed using a full normal imputation method to impute missing values Y_{n+1}, \dots, Y_N which assumes that the Y_i are iid from normal distribution with mean p and variance σ^2 . This method follows the following algorithm to generate the missing values.

This full normal imputation method without rounding incorrectly assumes a normal distribution and can sometimes yield implausible imputed values (above 1 or below 0). However, it produces an unbiased estimate of the probability of success p .

Allison (2005) [9] showed that this approach can be extended to allow covariates in the model. Hence, using simulation studies, Allison showed that multiple imputation using linear regression performed well in estimating regression coefficients in different missing data scenarios (MCAR, MAR) even when compared to logistic regression. The added benefit of using the linear regression model is that it directly provides proportion differences along with their 95% CI after applying PROC MIANALYZE to the model fits from the M multiply imputed datasets. This approach will follow the three steps described below:

Step 1: A multiple regression model: $Y_i = \beta_0 + \beta_1 X_1 + \beta_2 X_2 + \beta_3 X_3 + \dots + \beta_c X_c + \epsilon_i$, $\epsilon_i \sim N(0, \sigma^2)$ where Y_i represents the indicator for clinical improvement and X_c are the covariates described in Section 8.4.1 to be used in the multiple imputation model to generate M multiply imputed datasets.

Step 2: A linear regression model $Y_i = \beta_0 + \beta_1 trt + \beta_2 cstday5 + \epsilon_i$ will be fit on each of the M multiply imputed datasets with trt defined as 0 for Azithromycin and 1 for Placebo and $cstday5$ defined as the study day that D5V occurred on centered at the planned study day, i.e.; $cstday5 = stday5 - 5$. The study day for D5V covariate is centered to its planned study day to facilitate interpretation of the estimates.

Step 3: The final clinical improvement estimates will be obtained by combining M estimates of composite cure estimates using PROC MIANALYZE as described in in Section 8.4.1. The difference in rates of clinical improvement for placebo compared to azithromycin ($p_p - p_a$) when study day of D5V is 5 will then be obtained by β_1 . The rate of clinical improvement for placebo will be estimated as $p_p = \beta_0 + \beta_1$ and the rate of clinical improvement for azithromycin will be obtained by $p_a = \beta_0$ when the study day for D5V is 5. The two-sided 95% CI for the rates of clinical improvement and difference in rates in clinical improvement will use estimates from the linear regression with multiple imputation.

Rates of clinical improvement for each treatment group along with their 95% CI, a point estimate of the difference in rates of clinical improvement at D5V along with 95% CI obtained from linear regression with multiple imputation model as described above will be provided in Table 21 for D5V using the ITT analysis population.

The null hypothesis will be rejected and non-inferiority of placebo versus azithromycin with respect to clinical improvement on at D5V using a non-inferiority margin of 12.5% will be concluded if the lower bound of the 95% CI for the difference in rates of clinical improvement for azithromycin relative to placebo is greater than -12.5%. An individual listing of observed values of clinical improvement is provided in Listing 16.

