#### **11.4.1 Primary Analysis**

The non-inferiority of placebo versus azithromycin with respect to clinical improvement on at Visit 3 (as defined in Section 3.2.1), using a non-inferiority margin of 12.5%, will be determined for the ITT analysis population using a 95% confidence interval of the difference in proportions of clinical improvement as constructed using multiple imputation of clinical improvement with linear regression. The study Day that Visit 3 occurred on will be included as a covariate. A lower bound of the confidence interval greater than -12.5% will result in the conclusion of non-inferiority of placebo. At minimum, the imputation model will utilize available information collected at baseline and any completed study visits. Further details of the imputation model will be described in the SAP.

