  monotone regression(clinimprove_D5V) = &&modelVars_&i;
```

```
run;
```

```
%end;
```

imp_g&i will be subset to contain only rows for the subjects with imputed clinical improvement and merged together and with ATP-5 data to create the twenty complete multiply imputed datasets

Step 2: Analysis model: This model will fit regression models to the 20 complete datasets to obtain parameter estimates for treatment success, clinical cure, microbiological success.

```
proc reg data= imp_g outest= out_clinimp_D5V covout noprint;
```

```
model clinimprove_D5V= trt cstday5/clb alpha=0.05;
```

```
by _imputation_;
```

```
run;
```

Step 3: Combine estimates from models in step 2 to obtain overall estimates summarized over 20 imputed datasets;

```
proc mianalyze data= out_clinimp
```

```
  _D5 alpha = 0.05;
```

```
modeleffects intercept trt cstday5;
```

```
ods output ParameterEstimates=parms_trts;
```

```
run;
```

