14.2 Efficacy Data

Table 20: Percentage of Subjects with Missing Data by Study Endpoint, Timepoint, and Treatment Group - ITT Analysis Population

Endpoint	Azithromycin (N=X)		Placebo		All Subjects (N=X)	
	n	%	n	%	n	%
D5V						
Clinical Improvement						
DOOR						
D11V						
Clinical Improvement						
DOOR						
D28V						
Clinical Improvement						
N = Number of subjects in the ITT population in the respective treatment group; n = Number of subjects with missing data.						

Table 21: Primary Analysis of Clinical Improvement on D5V - ITT Analysis Population

Analysis Population	Statistic	Azithromycin (N=X)	Placebo (N=X)
ITT	Subjects with non-missing clinical improvement on D5V– n (%)	x (x)	x (x)
	Subjects with one or more components of clinical improvement imputed on D5V– n (%)	x (x)	x (x)
	Percent rate of clinical improvement at D5V (95% CI) ^a	xx (xx, xx)	xx (xx, xx)
	Difference in rates (percent) of clinical improvement, placebo relative to azithromycin (95% CI) ^a	-	xx (xx, xx)
	Conclusion of non-inferiority of placebo to azithromycin ^b	-	Yes/No

N = Number of subjects in the ITT Population. Multiple imputation was used for missing values.

^a95% CIs were obtained from linear regression model following multiple imputation adjusting for study day of D5V. The rates and difference in rates of clinical improvement presented assume that study day of D5V is 5.

^bNon-inferiority of placebo was concluded if the lower bound of the 95% CI for the difference in proportions is greater than -12.5%.

Table 22: Analysis of Clinical Improvement on D5V - ATP-5 Analysis Population

[Implementation note: If the lower bound of 95% CI for the difference in rates of clinical improvement is greater than -12.5, annotate the interval with footnote c that states 'Lower bound of confidence interval greater than -12.5% (non-inferiority margin).']

Analysis Population	Treatment Group	Rate of Clinical Improvement			Difference in Rates		
		n	%	95% CI ^a	%	95% CI ^a	95% CI Miettinen–Nurminen ^b
ATP-5	Azithromycin (N=X)	x	xx	xx, xx	Reference	-	-
	Placebo (N=X)	x	xx	xx, xx	xx	xx, xx	xx, xx

N = Number of subjects in the ATP-5 analysis population. n = Number of subjects in ATP-5 population with clinical improvement at D5V.

^a95% CI obtained from linear regression adjusting for study day of D5V. The rates and difference in rates of clinical improvement presented assume that study day of D5V is 5.

^bThe CI from Miettinen–Nurminen did not adjust for study day of D5V.

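### The closing decision rule for the primary analysis (SAP 8.1.1) reverses the treatment contrast and contradicts the SAP's own hypotheses, coding and Table 21

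*SAP*

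**What the plan says.** SAP 8.1.1 states the non-inferiority criterion twice.

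- Early in the section, after hypotheses written as π(placebo) − π(azithromycin): "A lower bound of the CI greater than -12.5% will result in the conclusion of non-inferiority of placebo". This sentence does not itself name the contrast.
- At the end of the section, in the sentence that begins with rejection of the null, the condition for declaring placebo non-inferior is that "the lower bound of the 95% CI for the difference in rates of clinical improvement for azithromycin relative to placebo is greater than -12.5" percent.

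Between the two, Step 2 has "trt defined as 0 for Azithromycin and 1 for Placebo", and Step 3 says what β₁ estimates: "The difference in rates of clinical improvement for placebo compared to azithromycin", written there as p_p − p_a.

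The Table 21 shell reports the difference as placebo relative to azithromycin. Its footnote b says that non-inferiority of "placebo was concluded if the lower bound of the 95% CI for the difference in proportions is greater than -12.5" percent. Protocol 11.1 states the same hypotheses, and Protocol 11.4.1 gives the rule as "A lower bound of the confidence interval greater than -12.5% will result in the conclusion of non-inferiority of placebo".

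SAP 8.1.1 also says that this analysis alone supports the non-inferiority conclusion, and SAP 6.8 says the primary analysis has a single hypothesis test.

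**The concern.** A one-sided non-inferiority criterion depends entirely on the direction of the contrast. Applying a lower bound of −12.5 points to placebo minus azithromycin rules out placebo being worse by 12.5 points or more. Applying the same bound to azithromycin minus placebo rules out placebo being *better* by that much, which is not what the trial asks.

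The closing sentence is the fullest statement of when the null is rejected, and the contrast it names is the reverse of the one in the hypotheses. The shorter rules in SAP 8.1.1, Table 21 footnote b and Protocol 11.4.1 take their direction from surrounding text. The SAP therefore contains two statements, in one subsection, that can give opposite verdicts on the same data. SAP section 1 requires deviations from the SAP to be described and justified in the study report, so the correct analysis would formally depart from the sentence as written.

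SAP 8.2.2 runs the Day 11 and Day 28 ITT analyses by analogy with 8.1.1 and gives no bound in its text. The Table 23 and Table 25 shells, however, state the correct contrast and bound for those two visits.

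**Working it through.** **1. Direction in each place**

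| Place | Direction |
|---|---|
| Hypotheses: Protocol 11.1, SAP 5, SAP 8.1.1 | placebo − azithromycin |
| Coding, SAP 8.1.1 Step 2 (azithromycin 0, placebo 1) | β₁ = placebo − azithromycin |
| Estimate, SAP 8.1.1 Step 3 | p_p − p_a = β₁ |
| Code, SAP 8.4.1 ("modeleffects intercept trt cstday5") | combines that same β₁ |
| Table 21, difference row | placebo relative to azithromycin |
| Closing sentence, SAP 8.1.1 | **azithromycin relative to placebo** |

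The phrase is not used loosely in this SAP. Table 30 labels its row placebo relative to azithromycin, and its footnote names azithromycin as the reference. *X relative to Y* therefore means X minus Y.

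**2. Inputs for the size**

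- Margin 12.5 points and a two-sided 95% interval (SAP 8 and 8.1.1).
- 674 randomised 1:1, so 674/2 = 337 per arm. ATP-5 size 560, so 280 per arm (SAP 5 and 6.6). The plan's inflation step reproduces: 560/(1 − 0.169) = 674.
- 57.6% improvement on azithromycin (SAP 5).
- Assumed here: Wald interval without continuity correction, complete data, no study-day covariate.

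**3. Formula**

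Let d be the true placebo − azithromycin difference, p_a = 0.576, p_p = p_a + d, and SE = √[p_a(1 − p_a)/n + p_p(1 − p_p)/n]. The chance of concluding that placebo is non-inferior is:

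- intended rule: Φ((d + 0.125)/SE − 1.96)
- sentence as written: Φ((−d + 0.125)/SE − 1.96)

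At the null boundary with n = 337, d = −0.125 and p_p = 0.451, so SE = 0.0382.

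- Intended: Φ(0 − 1.96) = 2.5%.
- As written: Φ(0.250/0.0382 − 1.96) = Φ(4.58), which exceeds 99.99%.

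**4. Results, 337 per arm**

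| True placebo − azithromycin (points) | Intended rule | Sentence as written |
|---|---|---|
| −12.5 | 2.5% | >99.99% |
| −5 | 50.0% | 99.6% |
| −2 | 78.5% | 96.7% |
| −1 | 85.5% | 94.3% |
| 0 | 90.7% | 90.7% |
| +5 | 99.6% | 51.2% |
| +10 | >99.9% | 9.9% |

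At 280 per arm, −12.5 points gives 2.5% against >99.99%, and 0 gives 84.9% for both.

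A simulation of 400,000 trials at 337 per arm, using the pooled-variance interval of a linear regression, gave 2.3% against >99.99% at −12.5, 49.1% against 99.5% at −5, 90.6% against 90.5% at 0, and >99.9% against 9.8% at +10.

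**5. One data set, two verdicts**

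Suppose 45.1% improve on placebo and 57.6% on azithromycin, with 337 per arm. The half-width is 1.96 × 0.0382 = 7.5 points.

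- Placebo − azithromycin: −12.5 ± 7.5, that is −20.0 to −5.0. The lower bound is below −12.5, so non-inferiority is not shown.
- Azithromycin − placebo: +12.5 ± 7.5, that is +5.0 to +20.0. The lower bound is above −12.5, so the sentence as written concludes that placebo is non-inferior.

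**The case against.** The strongest reply is that this is a word-order slip which nobody would act on. The sentence opens by rejecting a null that the same section defines as placebo minus azithromycin, and it names non-inferiority of placebo versus azithromycin in the right order. A lower bound on the reversed contrast cannot reject that null, so the literal reading contradicts the sentence's own first clause. The code combines only the treatment coefficient, no azithromycin-minus-placebo interval is planned for any output, and the Yes/No row of Table 21 sits directly under the correct contrast. The error rates above therefore belong to a procedure that would not be run. The Day 11 and Day 28 analyses are also protected by their own table shells.

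Most of this stands, and it limits the weight of the point. The figures are not the trial's operating characteristics, and the slip does not spread to the planned outputs for the later visits. It does not remove the contradiction. The SAP exists to fix the decision rule in advance, and the fullest written form of that rule conflicts with the hypotheses it is meant to test.

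**Conclusion.** The concern holds. The closing sentence of SAP 8.1.1 is wrong as written, because it reverses the contrast on the sole confirmatory test. It should be corrected, but it does not threaten the analysis if the coding, code and Table 21 shell are followed.

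Applied literally, the sentence would raise the chance of wrongly declaring placebo non-inferior at the null boundary from 2.5% to more than 99.99%. It would also cut the chance of success from above 99.9% to 9.9% if placebo were truly 10 points better. Those sizes rest on the Wald approximation and the assumptions listed with the inputs; imputation and the study-day covariate are ignored. The reversal itself rests on the text alone and needs no assumption.

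**What to change.** In the closing decision sentence of SAP 8.1.1, reverse the order of the arms so that the difference is the one for placebo relative to azithromycin, and add (β₁ = p_p − p_a) so that the rule points to the coefficient reported in Table 21. The bound stays at −12.5 points.

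The cost is one phrase in the SAP. The protocol, code, table shells, data, alpha and sample size do not change.

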8.2. Secondary Efficacy Analyses

8.2.1. Analyses of Clinical Improvement at D5V using ATP-5 Analysis Population.

The ATP-5 analysis population will have no missing values of clinical improvement, therefore the analysis of clinical improvement at D5V will be performed using a linear regression without multiple imputation with treatment group and centered study day of D5V as a covariates ($Y_i = \beta_0 + \beta_1 trt_i + \beta_2 cstday5 + \epsilon_i$) for subjects in the ATP-5 analysis population. The rate of clinical improvement in the placebo group will then be

estimated by $p_p = \beta_0 + \beta_1$ and the rate of clinical improvement in the azithromycin arm will be provided by $p_a = \beta_0$ assuming that the study day of D5V is 5.

The estimate for the difference in rates of clinical improvement given that study day of D5V is 5 will be provided by β_1 and its 95% CI will be calculated first by using the 95% CI for β_1 from the linear regression model above. As a sensitivity analysis, the 95% CI for the difference in rates of clinical improvement will be recalculated using the Miettinen–Nurminen (MN) method [13] from PROC FREQ with RISKDIFF (CL=MN) in SAS without adjusting for study day of D5V.

Rates of clinical improvement for each treatment group, a point estimate of the difference in rates of clinical improvement at D5V along with their 95% CIs obtained methods described above will be provided in [Table 22](#) using the ATP-5 analysis population. If the lower bound of the 95% CI for the difference in rates of clinical improvement is greater than -12.5%, it will be annotated by a footnote c.

8.2.2. Analysis of Clinical Improvement at D11V and D28V Using ITT Analysis Population

Analysis of clinical improvement will be repeated for D11V and D28V using the ITT analysis population in an analogous manner as the primary analysis as described in Section 8.1.1.

The non-inferiority of placebo versus azithromycin with respect to clinical improvement on at D11V will be determined for the ITT analysis population using a 95% CI of the difference in proportions of clinical improvement as constructed using multiple imputation of clinical improvement with linear regression. The study day that D11V (or D28V) occurred on centered at the planned study day (11 for D11V and 28 for D28V) will be included as a covariate in the imputation model. The imputation model will utilize available information collected at baseline and any completed study visits as described in Section 8.4.1.

Rates of clinical improvement for each treatment group in the ITT population along with their 95% CI and a point estimate of the difference in rates of clinical improvement at D5V along with a 95% CI will be obtained using linear regression following multiple imputation and shown in [Table 23](#) for D11V and [Table 25](#) for D28V after adjusting for study day of D11V and D28V, respectively.

8.2.3. Analyses of Clinical Improvement at D11V and D28V Using ATP Analysis Populations

Analysis of clinical improvement will be performed for ATP-11 and ATP-28 analysis populations will be performed using the same approach used for ATP-5 described in Section 8.2.1 using linear regression model with treatment group and centered planned study day of the visit as covariates.

Rates of clinical improvement for each treatment group along with their 95% CI, a point estimate of the difference in rates of clinical improvement along with 95% CI obtained methods described in Section 8.2.1 will be provided in [Table 24](#) for D11V using the ATP-11 analysis population and in [Table 26](#) for D28V using the ATP-28 analysis population. If the lower bound of the 95% CI for the difference in rates of clinical improvement is greater than -12.5%, it will be annotated by asterisk symbol (*).

8.2.4. Sensitivity Analysis of Clinical Improvement, ITT Analysis Population

Robustness of the multiple imputation model for ITT analysis population will be assessed by using tipping point analysis using linear regression as described in Section 8.2.1 using linear regression adjusting for treatment group and centered study day of D5V (or D11V, D28V). A point estimate of the difference in rates of clinical improvement, placebo relative to azithromycin and its 95% CI from the linear regression model will be reported. The results of this sensitivity analyses will be provided in [Table 27](#) for D5V, [Table 28](#) for D11V and [Table 29](#) for D28V.

8.2.5. Analysis of Number of Days of Antibiotics Use at D11V and D28V Using ATP Analysis Populations

Using the ATP-11 and ATP-28 analysis populations, respectively, the mean number of days of antibiotic use from Day 1 until D11V or D28V will be computed based on the definitions from Section 6.5.5 for the placebo group and the azithromycin group, in addition to an estimated difference in means for the placebo group relative to the azithromycin group using the t-test and its associated 95% CIs calculated based on t-test. The significance of the difference in means will be tested by a t-test and results from the Satterthwaite method will be provided in [Table 30](#) and [Table 31](#). An individual listing of days of antibiotics use is provided in [Listing 16](#).

8.2.6. Analysis of Medically Attended Events at D11V and D28V Using ATP Analysis Populations

Proportions of subjects with one or more return visits to a physician's office or urgent care, one or more emergency department visits, or one or more hospitalizations for persistent or worsening LRTI at any time after randomization by D11V or D28V will be produced for D11V and D28V and results will be reported in [Table 32](#), [Table 33](#), and [Table 34](#). Tests for differences in proportions, placebo relative to azithromycin, will be given by Fisher's Exact Test. In addition, an estimated odds ratio and its associated 95% CI calculated using the Wald Method will be provided. [Listing 19](#) contains all medically attended visits while [Listing 20](#) provides a listing of all hospitalizations.

